3. BACKGROUND

a. Past Experimental and/or Clinical Findings

Chronic pain and opioid overdose are two critical public health problems in the US. About 25 million adults (11%) suffer from chronic daily pain and up to 8 million use opioids to manage chronic pain. Unfortunately, 46 people die daily from overdose of prescription opioids. For safe chronic opioid therapy for chronic pain, physicians monitor patients' adherence to prescription opioids, and reduce or discontinue the prescription as indicated. Yet, adherence and cessation are not easy for some patients and one reason is opioid craving, a strong desire or urge to use opioids. Our preliminary data show about 34% of patients on chronic opioid therapy report craving. Craving is strongly associated with opioid misuse and negative health outcomes. To date, we do not fully understand the underlying mechanisms of prescription opioid craving in chronic pain sufferers, and psychological treatment targets to reduce craving. Based on our pilot survey, patients endorsing craving reported greater pain catastrophizing than those endorsing no craving. Our other survey study also reported a positive link between pain catastrophizing and opioid craving in patients on chronic opioid therapy for chronic pain conditions. Although these findings propose a possibility that lowering pain catastrophizing may decrease opioid craving, cross-sectional observational studies are limited in investigating a causal association. Potentially, pain catastrophizing enhances stress-induced opioid

craving because stress-induced opioid craving is a well-established phenomenon in studies of addiction, and pain catastrophizing is associated with greater pain and emotional distress in patients with chronic pain. Therefore, the proposed project seeks to determine: a) the effect of pain catastrophizing on prescription opioid craving in patients on chronic opioid therapy for chronic pain and b) psychological (negative affect) and physiological (cortisol, norepinephrine) distress as potential mediating variables.

Findings from Past Animal Experiments

NA

4. RADIOISOTOPES OR RADIATION MACHINES

a. Standard of Care (SOC) Procedures

b. Radioisotopes

- i. Radionuclide(s) and chemical form(s)

NA

- ii. Total number of times the radioisotope and activity will be administered (mCi) and the route of administration for a typical study participant

NA

- iii. If not FDA approved: dosimetry information and source documents (package insert, Medical Internal Radiation Dose [MIRD] calculation, and peer reviewed literature)

NA

c. Radiation Machines – Diagnostic Procedures

- i. Examination description (well-established procedures)

NA

- ii. Total number of times each procedure will be performed (typical study participant)

NA

- iii. Setup and techniques to support dose modeling

NA

- iv. FDA status of the machine and information on dose modeling (if procedure is not well-established)

NA

d. Radiation Machines – Therapeutic Procedures

- i. Area treated, dose per fraction/number of fractions, performed as part of normal clinical management or due to research participation (well-established procedures)

NA

ii. FDA status of the machine, basis for dosimetry, area treated, dose per fraction and number of fractions (if procedure is not well-established)

NA

5. DEVICES USED IN THE STUDY

a. Investigational Devices (Including Commercial Devices Used Off-Label)

NA

Investigational Device 1	
Name:	NA
Description:	NA
Significant Risk? (Y/N)	NA
Rationale for Non-Significant Risk	NA

b. IDE-Exempt Devices

IND-Exempt Device 1	
Name:	NA
Description:	NA

6. DRUGS, BIOLOGICS, REAGENTS, OR CHEMICALS USED IN THE STUDY

a. Investigational Drugs, Biologics, Reagents, or Chemicals

Investigational Product 1	
Name:	NA
Dosage:	NA
Administration Route:	NA

b. Commercial Drugs, Biologics, Reagents, or Chemicals

Commercial Product 1	
Name:	NA
Dosage:	NA
Administration Route	NA
New and different use? (Y/N)	NA

7. DISINFECTION PROCEDURES FOR MEDICAL EQUIPMENT USED ON BOTH HUMANS AND ANIMALS

NA

8. PARTICIPANT POPULATION

a. Planned Enrollment

- (i) 156 participants (50% female) will be recruited at the Stanford Systems Neuroscience and Pain Lab.
- (ii) All participants will be enrolled at Stanford. Patients with chronic pain and opioid medication use will be enrolled.

(iii) Patients, aged at least 18 years old, visiting our pain clinic for chronic pain treatment will be recruited because we want to identify a psychological treatment target for prescription opioid craving and misuse in patients with chronic pain conditions.

(iv) We will partner with the Research Participant Engagement Program (RPEP) team for Honest Broker outreach. Potential participants are identified via STARR and invited by RPEP team (honest broker) on behalf of study team. See Section 16 for Honest Broker study invitation letters. We will be using Postal Mail and Research Registry honest broker outreach. For Postal Mail, study team may support the process by sticking pre-printed address labels (created by RPEP, the honest broker) on the envelopes.

b. Age, Gender, and Ethnic Background

Participants, aged at least 18 years old of both genders and all racial and ethnic backgrounds will be included.

c. Vulnerable Populations

NA

d. Rationale for Exclusion of Certain Populations

The pain catastrophizing protocols (Taub et al, 2016, Roditi et al, 2009) have been validated only for adults with chronic pain. This study will be the first to use this protocol in patients taking opioid pain medications for chronic pain management. If this study finds no safety concerns in adult patients with chronic pain and chronic opioid therapy, a future study can include children.

e. Stanford Populations

Laboratory personnel, employees, and/or students will not be specifically recruited, although they will be able to participate if they visit our clinic.

f. Healthy Volunteers

NA

g. Recruitment Details

We will use the Collaborative Health Outcomes Information Registry (CHOIR) system. Patients on the CHOIR OK-to-Contact list will be invited to complete the online screening survey. Additionally, our lab is affiliated with the Stanford Pain Management Center, through which providers can inform interested patients of our research study. If needed, we will be able to recruit participants through our existing Stanford research databases where participants have agreed to be contacted for future research and recruit through community advertisements (Facebook/Instagram, Reddit, Stanford Report, Craigslist).

We will partner with the Stanford Research Registry to invite potential arm 1, 2, and 3 participants from the following cohort lists:

Individuals 18 and over indicating a pain condition with local zip codes (starting with 94 or 95) = 211

Individuals 18 and over indicating a pain condition with all zip codes (for arm 3) = 465
Participants will receive an email invitation (attached in section 16) and then will be directed to complete our screening survey.

Potential participants will complete the online screening survey. Based on the screening survey results, we will invite eligible participants to a laboratory experiment.

We will partner with the Research Participant Engagement Program (RPEP) team for Honest Broker outreach. Potential participants are identified via STARR and invited by RPEP team (honest broker) on behalf of study team. See Section 16 for Honest Broker study invitation letters. We will be using Postal Mail honest broker outreach. For Postal Mail, study team may support the process by sticking pre-printed address labels (created by RPEP, the honest broker) on the envelopes.

For both the Postmail and Registry, the patient can either reach out to the research coordinator or complete the screening survey. If they reach out to the research coordinator, they will send our screening survey link. If they are eligible after completing the screening survey, a research coordinator will reach out to conduct a phone screening and confirm eligibility. If they complete the screening survey, if they are eligible, a research coordinator will reach out to conduct a phone screening and confirm eligibility.

Update 6/6/24: We will use the Pain Division Newsletter, a new IRB approved recruitment method for SNAPL, to recruit current and past participants, patients, and members of the public who are interested in research on chronic pain.

h. Eligibility Criteria

i. Inclusion Criteria

For study 1, 2, and 3,

1. At least 18 years old
2. Chronic opioid therapy at least 3 months
3. Any chronic pain conditions at least 3 months

ii. Exclusion Criteria

For study 1 and 2,

1. Current diagnosis of cancer
2. Other severe psychiatric and cognitive conditions (schizophrenia, delusional disorder, psychotic disorder, dementia, Parkinson's or dissociative disorder)
3. An skin conditions on the non-dominant hand (pain testing site)
4. Non-English speaker
5. No access to email or smart phone
6. (For saliva collection) Daily use of cortisol or benzodiazepines
7. Being pregnant
8. Needle phobia for blood draw
9. Current suicide thoughts

added for study 3-----

For study 3,

1. Current diagnosis of cancer
2. Other severe psychiatric and cognitive conditions (schizophrenia, delusional disorder, psychotic disorder, dementia, Parkinson's or dissociative disorder)
3. Non-English speaker
4. No access to email or smart phone
5. Being pregnant
6. Current suicide thoughts
7. Concurrent psychological treatments during the 15-day study period.

i. **Screening Procedures**

New recruitment method will be used, the Research Participant Engagement Program (RPEP). RPEP will use coded diagnoses and procedures, clinical records, demographics with embedded identifiers, medications, names, telephone numbers, home address, date of birth, date of service, date of diagnosis, emails, and MRNs to recruit via postal mail.

Potentially eligible patients will complete an online prescreening survey. The online screening survey will assess patients' chronic pain and other health conditions, pain medication use, and prescription misuse, and craving. For prescription misuse and craving, the PROMIS item bank for the misuse of prescription pain medication and the COMM will be administered. This study will invite people endorsing chronic pain at least 3 months, taking opioid pain medications at least 3 months, and no craving or craving at any frequency on the PROMIS craving item (i.e., I experienced cravings for pain medication). Name, email, and phone number will be collected to invite eligible participants for the study.

Based on the responses on the online prescreening survey, potentially eligible patients will be contacted via phone for additional explanation about the study and to assess eligibility. During the screening phone call, potentially eligible participants will be asked questions to ensure inclusion criteria have been met and with the exception of assessing for current suicidal thoughts, potential participants will be asked questions to ensure exclusion criteria are not met. Participants who are otherwise willing and eligible will be notified that there is one sensitive eligibility question that will need to be asked after they have provided informed consent. If the potential participant inquires about the eligibility question, the research staff will notify the participant that the question is on the topic of suicidal ideation and that no response is needed at this time.

Participants recruited for the Arm 1 and 2 (in-person) study will be invited to the laboratory and will receive informed consent. Once the participant has signed the informed consent form, the research staff will assess the participant for the exclusion criteria of current suicidal thoughts. If the participant reports current suicidal ideations, they will be ineligible for the study and the Suicidal Ideation Protocol will be followed (included in section 16). Participants found to be ineligible will be withdrawn from the study.

Participants recruited for the Arm 3 (on-line only) study will receive an electronic copy of the consent form and will receive information about the study over the phone. Once the participant has signed the consent form, the research staff will assess the participant for the exclusion criteria of current suicidal thoughts. If the participant reports current

suicidal ideations, they will be ineligible for the study and the Suicidal Ideation Protocol will be followed (included in section 16). Participants found to be ineligible will be withdrawn from the study.

j. Participation in Multiple Protocols

Participants will be okay to participate in other clinical trials except for clinical trials including pain self-management or psychological interventions. If a patient is interested in participating in other clinical trials including pain self-managements or psychological interventions, a patient will be informed of two options : the one will be participating in other studies after completing this study for 14 days and the other option will be not to participate in this study.

k. Payments to Participants

Participants will be compensated \$30 for Study 1, \$5 for daily survey for 14 days, \$5 for three at home saliva samples, and \$5 for completion of all study requirement. Therefore, when completing the whole study requirements, a participant receive a total of \$120.

Travel cost will be compensated: \$25 for people living within 60 miles and \$50 for people living beyond 60 miles.

Added for the Study 3, -----

For study 3, participants will be compensated \$25 for completing the baseline tasks (the 30 or 40-min survey, cognitive testing and blood pressure and HR measure), \$60 for completing the short-daily survey and blood pressure ($\$5 \times 12 \text{ days} = \60), and \$10 for completing a 10-min survey and HR measure at day 8, and \$20 for completing the final survey. When completing all the tasks, the participant will receive additional \$5. Therefore, the total compensation is up to \$120 ($=25+60+10+20+5$). Participants will receive check as compensation.

l. Costs to Participants

NA

m. Planned Duration of the Study

Participants will complete (i) the initial 2.5 hour-laboratory experiment (Study 1) and daily home practice of coping statement and daily survey (3-5 minutes, Study 2) for 14 days. (iii) This study estimates 3 years of data collection and 1 year of data analysis.

Added for study 3, -----

Participants will completed (i) the initial 45-60min baseline survey, cognitive testing, and resting blood pressure and HR measure, (ii) a brief daily survey, resting blood pressure and HR measure for 15 days and practicing a 5-min daily coping statement 15 days (only for the 50% of people who are assigned to the coping statement condition), (iii) a 10 min survey at Day 8 and blood pressure and HR measure, and (iv) 20 min-final survey and cognitive testing, and blood pressure and HR measure.

9. RISKS

a. Potential Risks

i. Investigational devices

NA

ii. Investigational drugs

NA

iii. Commercially available drugs, biologics, reagents or chemicals

NA

iv. Procedures

Participants may experience discomfort from blood draw such as bleeding, soreness, bruising and stinging at the site of the blood draw. Participants may experience physical discomfort in undergoing cold water pressor test. To minimize the risk of physical discomfort, we will use our standard laboratory protocol (4 Celsius, 2 minutes), which is shown to induce "temporary" discomfort.

Online only Arm 3 study-----

No risk of physical discomfort in Arm 3 study

v. Radioisotopes/radiation-producing machines

NA

vi. Physical well-being

NA

vii. Psychological well-being

None of the questionnaires pose a risk to the participants. It is possible that subjects may feel uncomfortable answering some questions on the questionnaires; this risk will be minimized by allowing participants to refuse to answer a question. Additionally, some participants undergo pain catastrophizing induction protocol. We will use a validated pain catastrophizing protocol (IRB 11689, Taub et al., 2017, and Roditi et al., 2009), which is proven to "temporarily" induce catastrophic thinking about pain. For daily practice of pain coping statement, we will have only pain catastrophizing reduction and control condition. Finally, we will obtain certificate of confidentiality to protect the privacy of research subjects by prohibiting disclosure of identifiable, sensitive research information to anyone not connected to the research except when the subject consents or in a few other specific situations.

Arm 3 (online only) study-----

None of the questionnaires pose a risk to the participants. It is possible that subjects may feel uncomfortable answering some questions on the questionnaires; this risk will be minimized by allowing participants to refuse to answer a question. Also, we will collect the heart rate data anonymously and heart rate data will be recorded only with research email account and study id.

In this Arm 3 protocol, we have pain catastrophizing reduction and control condition. So, the intervention arm may help to reduce catastrophic thinking related to pain. We will also ask people to report opioid craving and misuse. As a part of NIH study, certificate of confidentiality also apply to this protocol. Therefore, we can protect the privacy of research subjects by prohibiting disclosure of identifiable, sensitive research information to anyone not connected to the research except when the subject consents or in a few other specific situations.

viii. Economic well-being

<Enter text or "NA">

ix. Social well-being

NA

x. Overall evaluation of risk

Minimum

b. International Research Risk Procedures

NA

c. Procedures to Minimize Risk

We are minimizing risks of physiological discomfort by excluding someone with a history of vasovagal syncope from blood draw and a needle phobia. We will also check vital signs before the blood draw. We are minimizing risks of psychological discomfort by allowing participants to refuse to answer any questions. Additionally, we will monitor physiological states throughout the study procedures. An experimenter will monitor physiological states and make sure their values are all within normal limits by the end of the experiment. We will also obtain the certificate of confidentiality to protect the privacy of research subjects by prohibiting disclosure of identifiable and sensitive research information to anyone not connected to the research except when the subject consents or in a few other specific situations. Finally, this study use validated and standard laboratory procedures.

For both the in-person study (Arm 1 and 2) and the online-only study (Arm 3), participants will be assessed for current suicidal thoughts by research staff after the participant has signed the consent form. For the in-person study, the consent procedure occurs in-person and participants endorsing current suicidal thoughts will be ineligible for the study and the Suicidal Ideations Protocol (included in section 16) will be followed accordingly. For the online-only study, participants will be consented over the phone and participants endorsing current suicidal thoughts will be ineligible for the study and the Suicidal Ideations Protocol (included in section 16) will be followed accordingly. If a suicidal thought is expressed anytime even before the consent, we will activate "the suicidal ideation protocol."

Added 10/17/2024: In response to the adverse event at the end of September, the research

team will be available to accompany in-person participants to their cars after appointments to help ensure their safety.

A research coordinator and research assistant will review all the responses in free text-format questions daily and activate "The suicide Ideation protocol" as needed.

d. Study Conclusion

The experiment will terminate when all data has been collected from participants. An individual's participation will terminate at the point that all data is collected from that individual, if the protocol director decides to withdraw the subject, or if the patient wishes to withdraw from the study.

e. Data Safety Monitoring Plan (DSMC)

i. Data and/or events subject to review

Self-reported adverse events were collected at the study endpoint for Aim 1, 2, and 3 studies. Adverse events were reviewed as soon as participants reported any events on the REDCap, which sent automatic email notification to [name], PI and Clinical Research Coordinator.

ii. Person(s) responsible for Data and Safety Monitoring

[name] [name]

iii. Frequency of DSMB meetings

Yearly

iv. Specific triggers or stopping rules

Any SAEs that are probably or possibly related to this study

v. DSMB Reporting

Sent a yearly DSMB reporting to NIH

vi. Will the Protocol Director be the only monitoring entity? (Y/N)

Y

vii. Will a board, committee, or safety monitor be responsible for study monitoring? (Y/N)

N

f. Risks to Special Populations

NA

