No audio or video recording will occur. **Alternative Procedures or Courses of Treatment**

Participants are free to pursue the treatment of their choice at any time during and/or after the study.

f. Will it be possible to continue the more (most) appropriate therapy for the participant(s) after the conclusion of the study?

Participants are free to pursue the treatment of their choice at any time during and/or after the study

g. Study Endpoint(s)

Each participant will meet the study endpoint once he/she completes the daily survey for 14 days after Study 1 laboratory visit. The study will end once the target enrollment is reached.

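### Adverse events are solicited only at an endpoint defined by survey completion: no question is specified at lab exit or on withdrawal, and the endpoint does not fit Study 3

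*Combined protocol and SAP*

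**What the plan says.** **When participants are asked.** Section 9e (Data Safety Monitoring Plan), item i: "Self-reported adverse events were collected at the study endpoint for Aim 1, 2, and 3 studies". The same item describes handling after a report: "Adverse events were reviewed as soon as participants reported any events on the REDCap", with an automatic email to the study team.

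**What the endpoint is.** Section 2g: "Each participant will meet the study endpoint once he/she completes the daily survey for 14 days after Study 1 laboratory visit". No other participant-level endpoint is defined.

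**How else participation can end.** Section 9d allows it to end "if the protocol director decides to withdraw the subject, or if the patient wishes to withdraw from the study". No adverse-event question or exit contact is attached to either route.

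**What rests on the information.** The trigger in section 9e, item iv, is "Any SAEs that are probably or possibly related to this study". Section 8d makes the inclusion of children in a future study conditional: "If this study finds no safety concerns in adult patients with chronic pain and chronic opioid therapy".

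**Other safety routes.** Section 9c provides for lab monitoring: "An experimenter will monitor physiological states and make sure their values are all within normal limits by the end of the experiment". It also has staff read free-text answers daily, for the stated purpose of activating the suicidal ideation protocol.

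**The concern.** Whether an adverse event is found depends heavily on whether and when participants are asked. If the only planned question comes on completion, the people not asked are those who stopped, and some may have stopped because of a bad experience. Among those who are asked, minor, emotional or delayed reactions to the lab session have to be recalled after two weeks of other activity.

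Two statements in the protocol lean on this information. The trigger for related serious events can respond only to events that reach the team. The condition of no safety concerns in section 8d is weaker if systematic enquiry reached completers only. Timing also affects attribution. Section 2a randomizes participants among three conditions in Study 1 and again between two in Study 2. A single late question, with no onset date specified, makes it harder to judge which procedure an event followed.

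**Working it through.** The plan gives no figure on this point to reproduce. The check sets the sections side by side.

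**Step 1. Time of asking.** Section 9e(i) gives the study endpoint. The participant tasks described in sections 2a and 8m (lab visit, daily surveys, saliva samples, final survey) mention no adverse-event item. The endpoint is therefore the only solicitation time stated.

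**Step 2. Who reaches the endpoint.** Under section 2g it is met by completing the daily survey for 14 days after the lab visit. Section 9d recognizes withdrawal before that. Reading the two together, a participant who withdraws early has no specified occasion on which to be asked.

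**Step 3. Delay for lab-day events, Studies 1 and 2.** Blood draw, cold pressor test and, for those assigned to it, the catastrophizing induction all fall on the lab day. From there to the endpoint is 14 days. What that delay affects depends on the kind of event:

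| Kind of event | Route described | Does the 14-day delay apply? |
|---|---|---|
| Acute physical reaction in the lab | Continuous physiological monitoring; saliva samples up to 30 minutes after the cold pressor test; values checked before the session ends | No, largely observed |
| Psychological distress after the session | No question until the endpoint, unless volunteered | Yes, for solicited report |
| Delayed physical effect, such as soreness or bruising from the blood draw | No question until the endpoint, unless volunteered | Yes, for solicited report |
| Suicidal thoughts expressed in free text | Daily review | No |

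Section 9a(iv) itself anticipates lab-day discomfort: "Participants may experience physical discomfort in undergoing cold water pressor test".

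**Step 4. Study 3.** Sections 2a and 8m describe it as remote, lasting 15 days, with no lab visit and a final survey at the end. An endpoint counted from the Study 1 visit cannot apply. Section 9e nevertheless relies on the study endpoint for all three aims, so the Study 3 collection time is undefined.

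**Step 5. Possible size.** Section 8a plans 156 participants. No attrition rate is given and the 156 are not divided among the studies. For illustration only, number without a solicited report = assumed attrition × 156:

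- 10%: 0.10 × 156 = 15.6, about 16
- 20%: 0.20 × 156 = 31.2, about 31
- 30%: 0.30 × 156 = 46.8, about 47

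These are upper figures at each rate, since they suppose that every non-completer in every study goes unasked.

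**The case against.** The strongest reply is that the text is ambiguous and the safeguards are more than a single late question.

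- **Separate endpoints.** Section 9e speaks of Aim 1, 2 and 3 studies without defining the term. Each study might have its own endpoint, and Study 1's could be the lab day, where section 2c already places a debriefing. Since section 2g cannot cover Study 3, it may not be the full meaning of the endpoint in section 9e. This stands as a possibility, but no such endpoint is written down.
- **Silence is not exclusion.** A reader might infer that drop-outs are never asked. The documents do not say so; they only fail to provide for asking. The REDCap forms and attachments are not in the text supplied. Completing 14 days may also mean reaching day 14, so a few missed surveys need not mean a missed question. This stands, and limits the point to what is specified.
- **Events reach the team by other routes.** A reader might infer that all lab-day events depend on two-week recall. In-lab monitoring rules that out for acute physical reactions. Nothing restricts the serious-event trigger to endpoint data. Section 9c records an adverse event in late September that led to a change dated 10/17/2024, so at least one event was acted on, though how it was reported is not given. This stands. It shows that events can surface, not that they are sought systematically.
- **Bias by condition.** A reader might infer that losses fall mainly in the induction condition and bias an event-rate comparison. No differential drop-out is documented, section 9a calls the induction's effect temporary, and the Analysis Plan contains no adverse-event rates or comparisons. That inference is unsupported.
- **Burden and reactivity.** Risk is rated minimum (section 9a, item x), and a daily prompt about bad experiences could itself be reactive in a study of catastrophizing. This is a fair reason not to insist on a daily item.

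**Conclusion.** The point holds in limited form. As written, solicitation of adverse events is tied to an endpoint reached by completing the surveys. No question is specified at the end of the lab visit or on withdrawal, and the endpoint definition does not fit Study 3. This is more than missing detail, because the one collection rule that is stated gives poorer ascertainment than contacts the study already has. For Studies 1 and 2 the delay is about 14 days and concerns solicited reports of psychological or delayed reactions only.

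The conclusion assumes that section 2g supplies the meaning of the endpoint in section 9e for Studies 1 and 2, and that no unseen form adds a question. The number of participants affected cannot be stated from the documents. The consequence is weaker support among non-completers for the serious-event trigger and for the section 8d condition; the documents do not show that any event was missed. In a study rated as minimum risk, this should be corrected but does not undermine the trial.

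**What to change.** Amend section 9e so that a standard adverse-event question, with onset date, is asked:

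1. before the participant leaves the lab, for example at the debriefing;
2. at any withdrawal or early stop;
3. at the last scheduled contact, whether or not all surveys were completed.

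State these times separately for each study, and say how the aims named in section 9e map to Studies 1, 2 and 3. In section 2g, define the Study 3 endpoint as its day-15 final survey. Keep the REDCap alert. A brief item in the daily survey is optional, given the reactivity concern.

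The past tense in section 9e suggests that some collection may already be finished. If so, report the actual collection times by study and how many participants were not asked, and limit the safety conclusion to those who were.

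The cost is a small amendment, one or two extra questions per participant and a few more minor events to review.
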